3.2 Study plan

Visit	Screening/Baseline	Week 4 ^{a,b}	Week 8-10 ^c	Week 12 ^a	Week 16-18 ^c	Early Withdrawal
Day	-28 to 1	23-33		79-89		
Sign Informed Consent	X					
Medical History	X					
Inclusion /exclusion criteria	X					
Gynecologic Exam ^d	X			X ^e		X
Physical Exam ^f	X					
ECOG status	X					
Concurrent Medication	X			X		X
Chemistry/Hematology ^g	X					
Serum Hormone Measurements ^h	X	X	X	X	X	X
Completion of QOL questionnaires	X	X		X		X
Dispense study medication	X ⁱ					
Adverse Events		X		X		X

- a. May occur \pm 5 days from day 28 (week 4) or day 84 (week 12).
- b. Clinic visit is optional.
- c. Visit is only for patients with abnormal estradiol levels at week 4 or week 12. Test does not include testosterone levels. [If the week 4 or week 12 estradiol level is outside the postmenopausal range (or if there is a >10 pg/ml increase in estradiol levels in patients with an estradiol level above the post-menopausal range at baseline), a repeat sample will be sent within 4-6 weeks. Therefore, estradiol will be repeated by week 10 for a patient with an elevation at week 4, and by week 18 for a patient with an elevation at week 12.]
- d. The physician's assessment of the vaginal epithelium will include a 3-point scale to evaluate color, petechiae, friability and dryness.
- e. Performed sooner if patient drops out or experiences unexpected side effects
- f. Limited exam consisting of cardiac and lung auscultation and abdominal exam only
- g. Includes CBC with differential, AST, alkaline phosphatase, total bilirubin. Abnormal results will be followed up at the investigator's discretion as per standard of care.
- h. Includes estradiol levels for all patients and serum testosterone levels only for patients randomized to the testosterone cream arm.
- i. Must be done on Day 1.

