4. TREATMENTS

4.1 ESTRING

ESTRING (estradiol vaginal ring) is a slightly opaque ring with a whitish core containing a drug reservoir of 2 mg estradiol. Estradiol, silicone polymers and barium sulfate are combined to form the ring. ESTRING has the following dimensions: outer diameter 55 mm; cross-sectional diameter 9 mm; core diameter 2 mm. When placed in the vagina, ESTRING releases estradiol, approximately 7.5 µg/24 hours, in a consistent stable manner over 90 days. Estradiol is chemically described as estra-1,3,5(10)-triene-3,17β-diol. The molecular formula of estradiol is C₁₈H₂₄O₂, and the molecular weight of estradiol is 272.39.

One ESTRING should be inserted into the upper third of the vaginal vault, to be worn continuously for three months.

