4.2.1 Testosterone Cream Absorption and Pharmacokinetics

Extrapolating from the fact that systemic absorption of estrogens is robust after the topical administration of estrogen creams vaginally, absorption of testosterone cream through the vaginal mucosa would be expected to be significant as well, but the pharmacokinetics have not been well described.

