4.3 Doses and treatment regimens

- Testosterone Cream 1% micronized in velvachol - 0.5 gm of cream vaginally 3 times a week for total of 12 weeks of treatment
- ESTRING 2mg ring inserted vaginally once every 12 weeks

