4.4 Mechanism of drug storage and destruction

Study drugs will be obtained as a special order from the UCSF Pharmacy (in the case of the ESTRING) or from the UCSF Drug Product Services Laboratory (in the case of the testosterone cream). Due to the limited shelf life of testosterone cream, this will be prepared in

batches of a 10 patient supply. Both the ESTRING and the testosterone cream will be stored under appropriate conditions and dispensed by the investigational pharmacist at the UCSF Mt. Zion Infusion Center Pharmacy. When patients have completed their 12 weeks of study treatment, they will be advised to remove and discard the ESTRING. For patients on the testosterone cream arm, patients will be advised to discard any remaining study drug, or if they choose, to continue using the remaining cream until it gone. Therefore, documentation indicating study drug was destroyed is not applicable to this study.

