Appendix C.

APPENDIX D.: Blood Specimen Collection and Handling Instructions for Research serum estradiol assay

At baseline and Week 4, one sample will be collected for standard hormone testing at UCSF or Quest Diagnostic® labs (routine lab test), and a second sample will be collected for a specialized low-level estradiol assay (research lab test).

- The lab slip should specify that an extra sample of blood is to be collected for the study.
- At least 3-4 ml of blood is needed to create the research serum sample that will be sent for low-level estradiol assay.
- The study personnel responsible for obtaining the research sample from the lab should label the red top vacutainer tube with the patient's identification (patient number and patient initials), protocol number (067519), date and time of blood draw (dd-MMM-yyyy format for the date (i.e. 01-JAN-2003) and 24:00 hour clock format for the time).
- The **research lab sample** will be collected by the lab technician in a red top vacutainer at the time the standard hormone blood sample is collected using standard venipuncture techniques.

Serum Collection Tube:

1. 4-6 mL red top vacutainer tube

Specimen Transfer Tube:

1. Non-sterile polypropylene specimen tube (cryovial) with screw cap.
2. Freezer resistant specimen label to fit the cryovial.

Serum Collection and Shipping Instructions

1. Draw 3-4 mL of blood (yielding ≥ 0.5 mL of serum) into a red top vacutainer tube at each designated specimen timepoint using standard venipuncture techniques.
2. After collection, the study personnel will take the sample to the centrifuge.
3. Allow the blood to clot upright at room temperature for 30 minutes.
4. Centrifuge the sample for approximately 15 minutes.
5. Completely fill out the label with the corresponding patient's identification (patient ID number and patient initials), protocol number (067519), date and time of blood draw (dd-MMM-yyyy format for the date (i.e. 01-JAN-2003) and 24:00 hour clock format for the time) and affix it to one of the room temperature polypropylene specimen tubes.
 - A freezer resistant label should be used so that water or freezing temperatures do not destroy the label since samples must remain frozen until shipment

6. Draw off the supernatant and pipette 0.5mL – 1.5 mL of the serum into the properly labeled polypropylene specimen tube.

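### Hormone draws are not tied to exposure: the week-12 window runs to day 89 against 84 days of treatment, a week-12 elevation is repeated after planned treatment, and no record of last application or ring status is specified

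*Protocol*

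**What the plan says.** - **Draw window.** Section 3.2, footnote a, allows plus or minus "5 days from day 28 (week 4) or day 84 (week 12". The schedule shows days 23–33 and 79–89.
- **Treatment length.** Section 4.3 gives the cream as "0.5 gm of cream vaginally 3 times a week for total of 12 weeks of treatment" and the ring as "ESTRING 2mg ring inserted vaginally once every 12 weeks". Footnote i of section 3.2 has study medication dispensed on day 1.
- **End of treatment.** Section 4.4: "When patients have completed their 12 weeks of study treatment, they will be advised to remove and discard the ESTRING". Cream patients are told to discard what is left or, if they prefer, "to continue using the remaining cream until it gone". Neither instruction refers to the week-12 blood draw.
- **Release and absorption.** Section 4.1 says the ring releases estradiol "in a consistent stable manner over 90 days". For the cream, section 4.2.1 expects significant absorption, "but the pharmacokinetics have not been well described".
- **Failure and its confirmation.** Section 3.1 counts a patient as failing only if two consecutive collections at least four weeks apart are elevated. Under footnote c of section 3.2, an abnormal week-4 value is repeated by week 10 and an abnormal week-12 value by week 18.
- **What is recorded.** Appendix D, which covers the baseline and week-4 research samples, asks for the "date and time of blood draw". The section 3.2 schedule has no row for product use or ring status.

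**The concern.** Secondary objective 1 (estradiol and testosterone levels under treatment) and the primary failure count both rest on these samples. Two women drawn on day 88, both in line with the protocol, can differ in exposure: one may have had her ring removed on day 84 and the other may still be wearing it. One cream patient may be using up her tube and another may have thrown it away. Nothing in the protocol would let the analyst tell them apart afterwards.

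Because failure needs two consecutive high values, one sample taken off drug is enough to clear a patient whose elevation was caused by the drug. The same holds for a woman who quietly stops using the product but attends her draws. She is evaluable once she has a baseline evaluation and a week-4 draw (section 3.1), and she counts as a non-failure. No SAP could repair this later, since it cannot recover exposure data that were never collected.

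**Working it through.** **Step 1. Calendar (sections 3.2, 4.1 and 4.3; day 1 = start).**

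- Planned treatment: 12 × 7 = 84 days, so days 1–84.
- Week-12 window: 84 − 5 = day 79 to 84 + 5 = day 89, which is 11 permitted days. Days 85–89, 5 of the 11, lie beyond day 84.
- Stated ring release: 90 days. A ring left in place would still cover day 89; a ring removed on day 84 would not.

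**Step 2. The two routes to a failure.**

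| First elevated draw | Repeat (4–6 weeks later) | Relation to day 84 |
|---|---|---|
| Week 4, days 23–33 | Earliest 23 + 28 = day 51; latest 33 + 42 = day 75 (footnote c says by week 10, day 70) | Inside treatment |
| Week 12, days 79–89 | Earliest 79 + 28 = day 107; by week 18, 18 × 7 = day 126 | At least 107 − 84 = 23 days after |

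The early route is sound on exposure. On the late route the confirming sample always falls after planned treatment. For the ring it also falls beyond the stated 90-day release (107 − 90 = 17 days at the earliest). Exposure at that time is not fixed either, because leftover cream is permitted (section 4.4) and post-study treatment is unrestricted (section 4.5).

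**Step 3. The plan's own operating characteristics (sections 7.1 and 7.2).** An arm is called safe if at most 2 of the first 10 fail and at most 4 of 35 fail in total:

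P(safe | p) = Σ over a = 0, 1, 2 of Bin(a; 10, p) × P[Bin(25, p) ≤ 4 − a]

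| True failure rate p | Protocol | Recomputed |
|---|---|---|
| 5% | 98% | 96.4% |
| 10% | 70% | 71.4% |
| 25% | 5% | 3.9% |

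At p = 0.25 the terms are 0.0563 × 0.2137 + 0.1877 × 0.0962 + 0.2816 × 0.0321 = 0.0120 + 0.0181 + 0.0090 = 0.0391. The rule is reproduced within 2 percentage points throughout.

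**Step 4. Sensitivity to missed failures.** Let m be the share of true failures that the draw schedule fails to detect. The protocol gives no value, so m is an assumption. The observed rate is 0.25 × (1 − m).

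| m (assumed) | Observed rate | P(called safe) |
|---|---|---|
| 0 | 25.00% | 3.9% |
| 5% | 23.75% | 5.5% |
| 10% | 22.50% | 7.6% |
| 20% | 20.00% | 13.8% |

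Solving for P(safe) = 5% gives an observed rate of about 24.1%. The nominal level is therefore passed once about 4% of true failures are missed (1 − 24.1/25). This table shows how sensitive the rule is. It does not estimate how many failures the draw timing would hide.

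**The case against.** A reader might infer that the whole scheme pushes levels and the verdict one way, toward 'safe'. The documents do not support that, for four reasons.

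1. *Cream timing.* A draw at no fixed time after an application can fall near a peak as easily as near a trough, and the protocol says the kinetics are poorly described. This shows extra variation, not a signed bias.
2. *Days 85–89.* These days are not shown to be unexposed. The ring's stated release covers them if it is still in place, and leftover cream may be used. The count of 5 days in 11 is a calendar fact, not a measured loss of exposure.
3. *Main failure route.* A week-4 elevation repeated by week 10 lies wholly within treatment. The week-12 window touches the primary count only for elevations first seen at week 12, or where the week 8–10 repeat is missing.
4. *Size.* No figure in the protocol supports any particular missed share.

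All four stand. It is also fair to say that arms are tested separately, so unequal exposure between arms does not alter either verdict; that known early stopping leads to a termination visit (section 3.3.5); and that the case report forms are not shown. The accurate statement is that recording is not specified, not that it does not happen.

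The objection does not remove the lack of defined exposure at the week-12 draw, the post-treatment timing of the week 16–18 repeat, or the absence of any specified means of identifying affected samples.

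**Conclusion.** The point holds in a limited form. The protocol does not fix or specify recording of exposure at the hormone draws. Exposure is undefined on days 85–89, and the confirmation of a week-12 elevation comes at least 23 days after planned treatment ends. A bias toward 'safe' is supported for three situations only: samples taken off exposure, non-use that goes unrecognised, and elevations that first appear at week 12. For untimed cream draws the consequence is uncontrolled variation in estradiol and testosterone, direction unknown, which weakens secondary objective 1.

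The size of any effect on the verdict cannot be derived from the protocol. The rise from 3.9% to 5.5%, 7.6% or 13.8% rests on a true failure rate of 25% and on assumed missed shares of 5%, 10% and 20%. What it establishes is that the safety rule has little room for missed failures.

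**What to change.** 1. In section 3.2, set the planned week-12 blood-draw window to end no later than day 84, for example days 79–84.
2. Schedule cream-arm draws at one consistent interval after an application, stated in advance.
3. At every draw, record the date and time of the last cream application, or whether the ring is in place.
4. Report levels and failures with a sensitivity analysis limited to draws taken on exposure.
5. Reconcile section 3.1 (the two-collection definition), section 3.2 (footnotes a and c) and section 4.4, so that the exposure status intended at the week-12 and week 16–18 draws is clear. Shortening the window alone leaves the week 16–18 question open.

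The changes concern sampling and recording; the treatment regimen is left as it is. The cost is an amendment to the footnotes, a narrower visit window and two extra fields on the draw form.

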3.3 Selection of study population

3.3.1 Study selection record

Patients receiving an aromatase inhibitor for early breast cancer who have complaints of vaginal dryness, dyspareunia, or decreased libido will be invited to participate. For this study, decreased libido is defined as a patient having decreased interest in sexual intercourse, decreased sexual arousal, or inability to achieve an orgasm. Ongoing logs will be kept to document the number of patients who declined to participate or who were found to be ineligible for the study during the screening process.

3.3.2 Inclusion criteria

1. Patients with histologically or cytologically confirmed Stage I-III breast cancer who are taking an aromatase inhibitor as adjuvant hormonal therapy. Patient must have started the aromatase inhibitor at least 30 days prior to enrolling.
2. Postmenopausal status as defined by:
 - History of bilateral oophorectomy
 - OR
 - No menses for 12 months
 - A. If patient is amenorrheic due to ongoing use of a GnRH agonist, the patient must have a documented serum estradiol level in the post-menopausal range while on an aromatase inhibitor at some time in the past AND the serum estradiol level must be <30 pg/ml during the screening period.
 - B. If a pre-menopausal patient was rendered amenorrheic by adjuvant chemotherapy within the past 2 years, patient must have a documented serum estradiol level in the post-menopausal range while on an aromatase inhibitor at some time in the past AND the serum estradiol level must be <30 pg/ml during the screening period.
 - 3. Age ≥ 18 and ≤ 80 years old.
 - 4. Patient must have recovered from the side effects of previous chemotherapy, surgery, or radiation therapy for early breast cancer.
 - 5. Patient must be able to comprehend and give written informed consent.
 - 6. Ability to read English and complete quality of life questionnaires.

3.3.3 Exclusion criteria

1. History of radiation to the vaginal area
2. Concurrent treatment with any type of oral, injectable or topical form of estrogen or androgen therapy including natural supplements marketed as hormone replacement products
3. Initiation of topical moisturizers (for example, Replens), or herbal or alternative medicines to manage the symptoms of vaginal dryness while on study. Patients

who were previously using these products may continue them with the same usage pattern while on study.

4. Use of vaginal hormonal products (rings, inserts, creams, gels) containing estrogens or androgens within the past 30 days
5. History of an abnormal pap smear within the last 12 months
6. History of endometrial or ovarian cancer
7. Any episode of vaginal bleeding in the past 6 months that has not been evaluated by a gynecological exam and/or pelvic ultrasound
8. History of sexual dysfunction prior to diagnosis of breast cancer (Sexual dysfunction will be defined as loss of libido or inability to achieve orgasm for which patient sought medical attention or which patient felt significantly interfered with quality of life.)
9. Moderate or severe depression for which the patient is receiving ongoing psychological counseling and/or taking antidepressants, **and** for whom, in the investigators opinion may be interfering in the patients sexual function independent of the side effects of breast cancer and aromatase inhibitor use.
10. Use of any investigational agent for breast cancer within 3 weeks of study entry.
11. No liver dysfunction or history of an arterial thromboembolic event or venous thrombosis.

3.3.4 Criteria for Discontinuation

Treatment may be discontinued if subject experiences significant vaginal irritation or other side effect thought by the investigators to be related to either of the interventions.

This will be a two stage study. In stage 1, ten patients are enrolled in each arm. If 3 or more of the first 10 patients in an arm fail (i.e. have a “persistently elevated estradiol level” as defined in Section 3.1 Study Design), no more patients are enrolled in that arm and it is concluded that the treatment for that arm is not safe. Patients already enrolled in that arm will be notified and given the option of discontinuing treatment. In stage 2 an additional 25 patients are enrolled in the arms that were not closed after stage 1. A treatment is considered unsafe if a total of 5 or more patients in both stages have failed (i.e. have a “persistently elevated estradiol level” as defined above). Under the null hypothesis that the treatment is unsafe with true probability of failure (i.e. persistent elevation of estradiol above postmenopausal threshold) equal to 25% or greater, the probability of rejecting the null hypothesis falsely (i.e. concluding the treatment is safe when it is not) is 5%. The probability is 98% of concluding that the trial is safe when the true probability of failure is 5% and is 70% when the true probability of failure is 10%.

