Up to 80 patients will be randomized to receive either testosterone or ESTRING so that 35 evaluable patients will receive each treatment. Randomization will attempt to balance the number of patients in each group based on self reported or medically documented depression, use of antidepressants, relationship status (single vs. partnered). Estradiol will be measured at baseline, at 4 weeks, and at 12 weeks into the study. If a patient is subsequently found to have a serum estradiol level outside of the post-menopausal range on day 1 of the study before the intervention begins (despite having a post-menopausal value during screening labs), this patient will be allowed to stay on study, and the subsequent estradiol level must be > 10 pg/ml higher than the baseline value to be considered a significant elevation outside the post-menopausal range. If a patient has an estradiol level outside of the post-menopausal range on the week 4 draw, or if there is a > 10 pg/ml increase in estradiol levels in patients with a baseline value above the post-menopausal range as described previously, they will have an additional lab draw at week 8.

Statistical methods

The primary outcome variable for determining safety at the end of the study is serial serum estradiol measurement. The test statistic is the number of patients that have a persistently elevated estradiol level above the post-menopausal range as described above. In the medical literature, there are no data to suggest what is “safe” or “unsafe” in terms of postmenopausal breast cancer patients being exposed to levels of estrogen above the postmenopausal range for a short duration of time (such as 12 weeks). No data exist to suggest that short term exposure to levels of estrogen above the post-menopausal range for up to 12 weeks would impact breast cancer recurrences. Therefore, it is fairly arbitrary to conclusively state that a certain rate of patients experiencing a short term increase in estradiol exposure with either of the treatment interventions (ESTRING or testosterone cream) is safe or unsafe. Taking this into consideration and after consulting with a number of breast cancer experts, we will consider each intervention “safe” if no more than 25% of patients in each arm have persistently elevated serum estradiol levels above the postmenopausal range after exposure to either of the study interventions.

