3. STUDY PLAN AND PROCEDURES

3.1 Overall study design

This will be a single institution open label randomized Phase II study evaluating intravaginal testosterone cream vs. the Estring for vaginal dryness and/or decreased libido in early breast cancer patients treated with an aromatase inhibitor. Up to 80 early stage breast cancer patients will be enrolled over 36-48 months in order to have a total of 70 evaluable patients. To be considered evaluable, patients must complete their baseline evaluation and week 4 safety blood draw. Randomization of patients will attempt to balance the number of patients in each group based on self reported or medically documented depression, use of antidepressants, and relationship status (single vs. partnered). Patients will be randomized to a 12 week course of treatment with either:

- Testosterone Cream 1% micronized in velvachol - 0.5 gm of cream vaginally 3 times a week for total of 12 weeks of treatment
- Estring 2mg ring inserted vaginally once every 12 weeks

Patients will complete quality of life surveys including the CARES Sexual Interest and Sexual Dysfunction Subscales (Appendix A), which includes a single item sexual satisfaction measure previously tested by Ganz, at day 1 (baseline), week 4, and at the end of week 12 (the survey may be done either in the clinic, or at home and then mailed/faxed). Patients will undergo a gynecologic exam at baseline and at the end of week 12 (or sooner if they withdraw from the study or experience unexpected side effects). During this exam, the vaginal epithelium will be assessed using a 3-point scale evaluating color, petechiae, friability and dryness (Appendix B). Within each treatment group, composite scores of the vaginal epithelium at baseline will be compared to composite scores at study termination.

Serum estradiol assays sent to the UCSF clinical laboratory are sent out to Quest Diagnostics, which uses extraction chromatography RIA for their ultra-sensitive estradiol. Day 1 and week 4 samples will also be stored temporarily and then sent in batches to a specialized research lab which has developed an assay to quantify low levels of estradiol found in post-menopausal women. This assay is a radioimmunoassay after ether extraction, and has a sensitivity limit of 3pmol/l. Serum testosterone levels will also be sent to Quest, which uses an ultrasensitive testosterone measurement which is run by liquid chromatography tandem mass spectrometry.

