7.6 Data and safety monitoring plan

One of the principle investigators will meet with a trial coordinator on a weekly basis to review AEs, complete reporting forms, and determine if AEs were treatment related, disease related or unknown. Adverse events and serious adverse events will be reported monthly in the UCSF Breast Cancer Site Committee. This committee consists of a minimum of three medical oncologists specializing in the care of breast cancer, a radiation oncologist, a statistician, a breast cancer surgeon and several basic scientists with expertise in cancer biology. During this meeting, an ongoing account of AEs and SAEs will be reviewed and any unexpected toxicities will be discussed. The group will then address whether the AEs, SAEs, or unexpected toxicities justify early closure of the study.

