9.3 Written informed consent

It is the responsibility of the investigator to ensure that each patient reads, understands, and signs a document of informed consent before the subject can participate in the study. The contents and process of obtaining informed consent should be in accordance with all applicable regulatory requirements.

The subject's signed and dated informed consent(s) must be obtained before conducting any procedure specifically for the study. The subject will receive a copy of the signed and dated form, and the original will be retained in the site's study records. It is the responsibility of the investigator or his/her designee to inform the patient that participation in the study is entirely voluntary, and that consent regarding study participation may be withdrawn at any time without penalty or loss of benefits to which the subject is otherwise entitled.

If modifications are made to the protocol or informed consent according to local requirements, the new version will be approved by AstraZeneca.

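### The safety rule stops enrolment and informs patients at 3 failures in the first 10, but is silent when a fifth failure in stage 2 makes the unsafe verdict equally final

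*Protocol*

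**What the plan says.** Sections 3.3.4 and 7.2 of the protocol carry the same two-stage rule, applied to each arm separately. A failure is a persistent estradiol elevation as defined in section 3.1.

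- **Stage 1.** With 3 or more failures among the first ten patients, "no more patients are enrolled in that arm and it is concluded that the treatment for that arm is not safe". The next sentence adds: "Patients already enrolled in that arm will be notified and given the option of discontinuing treatment".
- **Stage 2.** "In stage 2 an additional 25 patients are enrolled in the arms that were not closed after stage 1". Then: "A treatment is considered unsafe if a total of 5 or more patients in both stages have failed". No enrolment stop and no notice is attached to this second count.

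The synopsis speaks of the end of the trial: "The primary outcome variable for determining safety at the end of the study is serial serum estradiol measurement". The monitoring plan in section 7.6 provides a monthly committee review of adverse events: "The group will then address whether the AEs, SAEs, or unexpected toxicities justify early closure of the study". It mentions neither the estradiol failure count nor the limit of five. Section 9.3 gives every patient the usual right that "consent regarding study participation may be withdrawn at any time without penalty".

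**The concern.** Two counts lead to the same verdict, but only the first leads to action. Failures accumulate and are never taken back, so once an arm has five, the remaining stage 2 patients cannot change the primary conclusion for it. Read literally, the arm still fills to 35.

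The primary objective is safety in women whose cancer treatment works by suppressing estrogen, and section 4.1.3 records that the ESTRING package contraindicates estrogens in known breast cancer. The protocol itself treats a stop and a notice as the proper response to an unsafe verdict at 3 of 10. An arm that narrowly passes that look and then fails has no such response written for it. What is at stake is avoidable exposure of new patients, and whether those on treatment are told. The validity of the test is not at stake.

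**Working it through.** **Inputs.** Sections 3.3.4 and 7.2: 10 patients in stage 1, close at 3 or more failures; 25 more in stage 2; unsafe at 5 or more in total. Section 7.1: null rate 25%, power quoted at 5% and 10%. Section 3.1: "Up to 80 early stage breast cancer patients will be enrolled over 36-48 months". Section 3.2, note c: an elevation at week 4 is repeated by week 10, one at week 12 by week 18. All enrolled patients are taken as evaluable.

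**1. Reproduce the stated design.** With X1 ~ Bin(10, p),

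P(safe) = Σ over x = 0, 1, 2 of P(X1 = x) · P(Bin(25, p) ≤ 4 − x).

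At p = 0.25: 0.0563 × 0.2137 + 0.1877 × 0.0962 + 0.2816 × 0.0321 = 0.0120 + 0.0181 + 0.0090 = 0.039.

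| True rate | P(safe) | Stated |
|---|---|---|
| 25% | 0.039 | 5% (nominal level) |
| 10% | 0.714 | 70% |
| 5% | 0.964 | 98% |

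These agree to within two points. A final limit of 6 would give 0.0885 at 25% and a limit of 4 would give 0.527 at 10%, so five is the intended limit.

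**2. How often the unsafe verdict comes in stage 2.** P(pass stage 1, then reach five) = 1 − P(close at stage 1) − P(safe).

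- 25%: 1 − 0.474 − 0.039 = 0.486, which is 0.486/0.961 = 51% of all unsafe verdicts
- 10%: 1 − 0.070 − 0.714 = 0.215
- 5%: 1 − 0.012 − 0.964 = 0.025

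**3. When the fifth failure falls.** Given x ≤ 2 failures in stage 1, the fifth failing patient is number 10 + k with probability C(k−1, 4−x) p^(5−x) (1−p)^(k−5+x), for k = 5−x to 25. The earliest case is x = 2 and k = 3, which is patient 13. The mean position is 23.0 at 25% and 28.3 at 10%, leaving 12.0 and 6.7 women still to be enrolled.

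**4. Allow for confirmation time.** Assume even accrual split equally between arms: 80/48/2 = 0.83 to 80/36/2 = 1.11 women per arm per month. Ten weeks (2.3 months) gives 1.9 to 2.6 women and eighteen weeks (4.2 months) gives 3.5 to 4.6, so about 2 to 5 enter before the failure is known. Enrolments after that point:

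| True rate | If it happens (lag 2; lag 5) | × probability | Per arm, unconditional |
|---|---|---|---|
| 25% | 10.1; 7.3 | 0.486 | 4.9; 3.6 |
| 10% | 5.0; 3.0 | 0.215 | 1.1; 0.6 |
| 5% | 3.8; 2.1 | 0.025 | about 0.1; 0.05 |

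If the other arm has closed and accrual here doubles, up to about 9 women may enter meanwhile. The conditional figures are then 4.1 (25%) and 1.2 (10%), or about 2.0 and 0.3 unconditionally.

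**5. Effect of stopping at five.** An arm with five failures is unsafe whether or not the rest are enrolled, so P(safe) is unchanged at every rate. Recomputing with the stop gives 0.039 at 25% and 0.714 at 10%, as in step 1.

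**6. Cost in secondary power.** By noncentral t, with SD of change 0.74 (section 7.3, correlation 0.8) and the arm closing at about 26 patients: paired power for 0.41 falls from 0.89 to 0.77, and two-sample power for 0.57 falls from 0.89 (35 v 35) to 0.83 (26 v 35). For that two-sample comparison section 7.3 quotes 80% and the synopsis 90%; the SD of 0.74 gives 0.89.

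**The case against.** The strongest reply is that this is a coherent design: one formal look at ten, a fixed second stage and a final limit. Its stated properties reproduce. Stopping at the deciding failure is a refinement that many two-stage designs leave out. That is fair, and it is why this is a gap in conduct and not a statistical error.

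Second, a route to closure exists. Section 5.1.1 counts abnormal laboratory findings as possible adverse events, an investigator reviews events weekly, and the committee in section 7.6, which includes a statistician, may close the study. A reader might therefore go too far in inferring that the protocol requires enrolment to continue, or that patients are kept in the dark. The text does not say so: it is silent, the total of 80 is a ceiling, and the consent pages and Appendix C schema are not available. What remains is that closure is left to judgement and no stop or notice is tied to five failures, whereas both are mandatory at 3 of 10.

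Third, the later patients have value. The CARES power assumes 35 per group, and section 7.4 assumes 35 samples for the assay comparison. Section 7.1 also calls the 25% limit fairly arbitrary and finds no data linking 12 weeks' exposure to recurrence. This stands as a trade-off, but the protocol does not give it as a reason, and it accepts the same loss at stage 1.

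Fourth, few women would receive the notice. With 12 weeks' treatment and 0.83 to 1.11 entries a month, only about 2 to 3 per arm are on treatment at once. This is correct. Most of the benefit lies in the enrolment stop.

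**Conclusion.** The gap is real and of minor to moderate importance. Sections 3.3.4 and 7.2 give no action for a fifth failure in stage 2, although that verdict is as final as the one at stage 1, and at a true rate of 25% about half of unsafe verdicts arise there. The expected avoidable enrolment at that rate is about 3.6 to 4.9 women per arm.

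It would be wrong to read the 10% figures as women enrolled in an arm known to be unsafe. A 10% rate lies under the protocol's alternative, so five failures there give a false unsafe verdict; the 0.6 to 1.1 enrolments are ones the rule's own verdict would no longer justify, and are not harm by the 25% standard. At 5% the matter is negligible. Nor is the right to withdraw in doubt, since section 9.3 secures it.

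The figures assume independent failures at a constant rate, even and equal accrual, full evaluability, and confirmation in roughly the order of enrolment.

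**What to change.** Add to sections 3.3.4 and 7.2: *If a fifth failure in an arm is confirmed during stage 2, enrolment in that arm stops, the treatment is concluded not to be safe, and patients already enrolled in the arm are notified and offered discontinuation, as in stage 1.* Someone must keep a running count per arm; the weekly review in section 7.6 is a natural place.

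No extra blood draws are needed, and neither the false-safe probability nor the power of the safety test changes. The price is less CARES and assay-comparison data in a closed arm, with the CARES power losses shown in the working. If the investigators prefer to complete stage 2 for those data, the protocol should say so and give the reason, and the notice to patients should still be added.
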